5.5.1.1. Mirvetuximab Soravtansine-Related Adverse Events

Dose modifications for MIRV-related AEs are described in [Table 3](#).

Table 3: Dose Modifications for Mirvetuximab Soravtansine-related Adverse Events

Severity Grade (CTCAE v5.0)	Dose Modifications for MIRV ^a
Hematological	
Neutropenia	
Grade 2 and Grade 3	Hold drug until ANC is $\geq 1.5 \times 10^9/L$ (1500 μL) and resume at the same dose level
Grade 4	Hold drug until ANC is $\geq 1.5 \times 10^9/L$ (1500 μL) and then resume at one lower dose level
Febrile neutropenia Grade 3 or 4 (with a single temperature reading $\geq 38.3^{\circ}C$ or a sustained temperature of $> 38^{\circ}C$ for > 1 hour)	Hold drug until ANC is $\geq 1.5 \times 10^9/L$ (1500 μL) and then resume at one lower dose level
Thrombocytopenia	
Grade 2 and Grade 3	Hold drug until PLT count is $\geq 100 \times 10^9/L$ (100,000/ μL) and resume at same dose level
Grade 3 associated with clinically significant bleeding that requires transfusion therapy and Grade 4	Hold drug until PLT count is $\geq 100 \times 10^9/L$ (100,000/ μL) and then resume at one lower level
Non-hematological	
Nausea and Vomiting	
Grade 3 (despite use of optimal antiemetics)	Hold drug until resolved to \leq Grade 1, then resume at one lower level
Grade 4	Permanently discontinue
Diarrhea	
Grade 3 (despite use of optimal antidiarrheal treatment)	Hold drug until resolved to \leq Grade 1, then resume at one lower level
Grade 4	Permanently discontinue
Ocular Disorders	Refer to Section 5.5.2
Noninfectious Pneumonitis	Refer to Section 5.5.3
Infusion-related Reactions	Refer to Section 5.5.5

Table 3: Dose Modifications for Mirvetuximab Soravtansine-related Adverse Events (Continued)

Severity Grade (CTCAE v5.0)	Dose Modifications for MIRV ^a
All Other Non-hematological Toxicities (except AEs related to underlying disease, Grade 3 fatigue, isolated symptomatic Grade 3 biochemistry laboratory abnormalities that last for < 7 days including electrolyte abnormalities that respond to medical intervention)	
Grade 3	Hold drug until resolved to \leq Grade 1, then resume at one lower level For any Grade 3 hepatic toxicity that does not resolve to baseline within 7 days, an abdominal CT scan must be performed to assess whether it is related to PD.
\geq Grade 3 Cardiac events (excluding Grade 3 hypertension)	Permanently discontinue
Grade 4 non-hematological toxicities	Permanently discontinue

Abbreviations: AE = adverse event; ANC = absolute neutrophil count; CT = computed tomography; CTCAE = common terminology criteria for adverse events; MIRV = mirvetuximab soravtansine; PD = progressive disease; PLT = platelets.

^a Failure to meet retreatment criteria within 1 cycle (21 days) after the missed dose due to insufficient recovery from a treatment-related toxicity will result in treatment discontinuation unless otherwise specified in the management guidance for a particular toxicity.

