5.5.2.2. Management and Dose Modification Guidelines

If a patient develops ocular symptoms of any grade, the patient is required to have a complete examination by an ophthalmologist. If a patient develops \geq CTCAE Grade 2 ocular symptoms, treatment with MIRV must be interrupted. Treatment should not be interrupted solely for Grade 2 ocular signs (eg, Grade 2 keratopathy) unless they are also associated with Grade 2 ocular

symptoms. Treatment with MIRV may resume if ocular symptoms improve to Grade 1 or baseline within 28 days of the next scheduled MIRV dose (refer to [Table 5](#) for details). If ocular symptoms last longer than 28 days, resumption of MIRV, with or without dose reduction, may be considered for those patients who have experienced clinical benefit if agreed upon between the Sponsor and the Investigator. Subsequent eye examinations will be scheduled to occur in every other cycle going forward, from the time that the AE was initially reported and at either the End of Treatment (EOT) Visit or 30-Day Follow-up Visit after treatment discontinuation, even if the results of the patient's ocular exam show no obvious clinical findings. Management of treatment-emergent ocular AEs with inflammatory characteristics should include corticosteroid eye drops and/or other measures as indicated by an ophthalmologist.

Table 5: Management of Ocular Symptoms

Severity Grade (CTCAE v5.0)	Management	Guidelines for MIRV Dose Modifications
Grade 1	Complete eye exam as outlined in Schedule of Assessments (Table 2) Monitor for worsening symptoms	Continue MIRV dosing
Grade 2	Complete eye exam as outlined in Schedule of Assessments (Table 2) Repeat complete exam as clinically indicated Patients should have weekly symptomatic ocular assessments by the Investigator until the symptoms resolve to Grade 1 or baseline or are deemed to be irreversible by the Investigator	Hold MIRV dosing until AE has resolved to Grade 1 or better Patients with ocular symptoms lasting < 14 days may be allowed to resume MIRV at the same dose level Patients with ocular symptoms lasting \geq 14 days but no more than 28 days may resume MIRV at one lower dose level Recurrence of Grade 2 toxicity on subsequent cycles despite best supportive care will require a MIRV dose reduction of one dose level

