5.5.4. Management of Electrolytes Imbalance

Prompt attention should be given to the correction of potential electrolytes imbalance, especially hypokalemia and hypomagnesemia.

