7.10.1. Clinical Laboratory Panels

A list of clinical laboratory tests may be found in [Table 8](#).

Table 8: Clinical Laboratory Tests

Hematology	Serum Chemistry	Urinalysis (Screening only)	Coagulation (Screening only)

 • Hematocrit • Hemoglobin • WBC (with 5-part differential) • Platelet count 	
 • Albumin • Alkaline phosphatase • ALT • AST • BUN or Urea • Calcium • Chloride • Creatinine • Glucose • Magnesium • Phosphorus • Potassium • Sodium • Total bilirubin 	
 • pH • Ketones • Protein • Glucose • Occult blood • Leukocyte esterase • Nitrite 	
 • PT or INR • aPTT

Abbreviations: ALT = alanine aminotransferase; aPTT = activated partial thromboplastin time; AST = aspartate aminotransferase; BUN = blood urea nitrogen; INR = international normalized ratio; PT = prothrombin time; WBC = white blood cell count.

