In addition, AEs may also include laboratory values that become significantly out of range. Such abnormal laboratory values or test results constitute AEs if they induce clinical signs or symptoms, are considered clinically significant (eg, cause study drug discontinuation or constitutes in and of itself an SAE, or require therapy), and should be recorded in the clinical database under the signs, symptoms, or diagnosis associated with them. In the event of an out-of-range value, the laboratory test should be repeated until it returns to normal or baseline or can be explained and the patient's safety is not at risk.

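### Protocol Table 3 spares short *symptomatic* Grade 3 biochemistry abnormalities from dose reduction but not asymptomatic ones; probably a slip for *asymptomatic*

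*Protocol*

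**What the plan says.** Protocol Section 5.5.1.1, Table 3, sets dose modifications for MIRV-related adverse events. In its last block, for all other non-hematological toxicities, a Grade 3 event means hold until Grade 1 or lower, then resume one level lower. Three things are excepted: events due to the underlying disease, Grade 3 fatigue, and "isolated symptomatic Grade 3 biochemistry laboratory abnormalities that last for < 7 days including electrolyte abnormalities that respond to medical intervention".

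Four other provisions bear on how this works:

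- **Table 4 (Section 5.5.1.2):** the levels are 6.0, 5.0 and 4.0 mg/kg AIBW. A patient at 4.0 who needs a reduction stops permanently. Re-escalation is not allowed.
- **Section 5.5.1:** before any dose, non-hematologic toxicity that may be drug-related must be Grade 2 or lower, or back to baseline. Ocular events and pneumonitis have stricter limits.
- **Section 8.1.1.1:** a laboratory value is an adverse event if it produces signs or symptoms, and also if such values "are considered clinically significant (eg, cause study drug discontinuation or constitutes in and of itself an SAE, or require therapy". A value without symptoms can therefore be an adverse event.
- **Section 5.5.4:** "Prompt attention should be given to the correction of potential electrolytes imbalance, especially hypokalemia and hypomagnesemia". It gives no dose rule and does not mention symptoms.

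**The concern.** Symptoms normally argue for more caution with dosing. Here the printed exception gives the lighter action to the patient with symptoms and the heavier, permanent one to the patient without. Sites must apply Table 3 as it stands, because Section 12.7 forbids prospective waivers.

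Two things are at stake for individual patients. One with a brief symptom-free abnormality could lose a dose level for good. Section 5.5.2.1 reports that exposure was related to response as well as to ocular events, so an unneeded reduction is not clearly harmless. One with a brief symptomatic abnormality could go back to full dose without first recovering to Grade 1.

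**Working it through.** The plan states no figure to reproduce. The check is a reading of the rule, plus the dose steps.

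**Step 1. Apply the row literally.** Take two patients at 6.0 mg/kg AIBW. Each has an isolated, MIRV-related, non-electrolyte Grade 3 chemistry value lasting under 7 days and recorded as an adverse event.

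| | With symptoms (themselves below Grade 3) | Without symptoms, but clinically significant |
|---|---|---|
| In the exception? | Yes | No |
| Recovery needed before the next dose | Grade 2 or lower, or baseline (Section 5.5.1) | Grade 1 or lower (Table 3) |
| Next dose | 6.0 mg/kg | 5.0 mg/kg, no re-escalation |

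With *asymptomatic* in the text, the two columns swap.

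**Step 2. Size of one reduction (Table 4).**

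- From 6.0: (6.0 − 5.0) / 6.0 = 16.7%.
- From 5.0: (5.0 − 4.0) / 5.0 = 20%.
- From 4.0: permanent discontinuation.

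**Step 3. Can the right-hand column occur?** Yes. Section 8.1.1.1 lists symptoms and clinical significance as alternatives, and its examples of significance include a need for therapy. A value with no symptoms, no clinical significance and no treatment may not be an adverse event at all, and Table 3 would then not reach it.

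**Step 4. Electrolytes.** The clause beginning with *including* can be read in two ways. It may be a subset of the symptomatic abnormalities, or it may except corrected electrolyte abnormalities whether or not there were symptoms. The anomaly is therefore clearest for non-electrolyte values.

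**Step 5. Compare with the protocol's other dose rules.**

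- **Ocular, Section 5.5.2.2:** "Treatment should not be interrupted solely for Grade 2 ocular signs (eg, Grade 2 keratopathy) unless they are also associated" with Grade 2 symptoms. Signs alone are treated more leniently than symptoms at the same grade.
- **Neutropenia, Table 3:** Grade 3 alone resumes at the same dose, but "Febrile neutropenia Grade 3 or 4 (with a single temperature reading" criterion met) resumes one level lower.
- **Thrombocytopenia, Table 3:** Grade 3 alone resumes at the same dose, but "Grade 3 associated with clinically significant bleeding that requires transfusion therapy and Grade 4" resume one level lower.
- **Pneumonitis, Section 5.5.3:** patients without symptoms may continue, while symptomatic Grade 2 is held.

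All four are lighter on the less complicated or symptom-free case. The biochemistry exception as printed runs the other way.

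**Step 6. Look for an explanation.** Sections 5.5.4 and 5.5.6, the protocol's summary of changes and the SAP neither explain nor correct the wording.

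**The case against.** The strongest objection is that this may not be an error in the plan at all. The point turns on one letter in wording that occurs once, and the text examined was machine-read from a PDF. Small reading differences are visible elsewhere: the approval year in the running header appears as 2021, 202 and 2022, and the sidedness of alpha is hyphenated in the synopsis but not in Section 10.1. This does not show that a letter was lost here, but it rules out certainty. It stands as a limit on confidence and makes checking the original the first step.

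The comparators are also imperfect. The ocular rule concerns interruption at Grade 2, not reduction at Grade 3. Fever and bleeding are complications rather than symptoms of the same finding. In Table 6, absence of symptoms is the definition of Grade 1 pneumonitis, so that is not a same-grade contrast. This stands too: the comparators make *asymptomatic* plausible but do not prove it.

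The affected group is small. Scheduled chemistry is drawn up to 4 days before Day 1 of each 3-week cycle (Table 2), so many short symptom-free rises would be seen only if extra tests were done. This also stands.

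Stronger readings are tempting but not supported:

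- A reader might infer that the documents establish a drafting error. They establish only what the supplied text says.
- A reader might infer a large effect from the number of chemistry tests in Table 8, or from a run of repeated reductions ending in discontinuation. A count of test names is not a count of events, and the documents give no frequency for such events.
- A reader might infer that patients with symptoms are redosed without restraint. Section 5.5.1 still applies to excepted events, Grade 4 non-hematological events mean discontinuation, and Section 5.6.1 lets the Investigator stop treatment at any time.

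**Conclusion.** The point holds as a minor one. As supplied, the Table 3 exception runs in the wrong direction: a short drug-related Grade 3 biochemistry abnormality keeps its dose if symptomatic, while the same abnormality without symptoms, once recorded as an adverse event, requires a permanent one-level reduction.

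That *symptomatic* should read *asymptomatic* is probable, not proven. Confidence is low until the word is checked. The conclusion assumes that the supplied text matches the original and that the value counts as a MIRV-related adverse event.

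The reach is limited to isolated Grade 3 values lasting under 7 days, mainly non-electrolyte ones. The number of patients is unknown. The ORR analysis, its null rate and its decision rule are unaffected.

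**What to change.** 1. Check the word against the original protocol, and have the sponsor's medical lead confirm the intent.
2. If the original reads *symptomatic* and this was not intended, change it to *asymptomatic*.
3. In the same edit, free the electrolyte clause from the adjective. For example, except isolated Grade 3 biochemistry abnormalities of under 7 days that are either (a) asymptomatic, or (b) electrolyte disturbances corrected by treatment, with or without symptoms. A bare change of word could otherwise push promptly corrected symptomatic electrolyte events into mandatory reduction.
4. If *symptomatic* was intended, give the reason in Section 5.5.1.1.

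**Cost.** One table row and a note to sites, with no new procedures or patients. It can go into the next amendment, and Section 12.7 allows for expedited ethics review of minor changes.

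**Downside, which the medical lead must accept.** Short asymptomatic Grade 3 values, including hepatic ones, would no longer force a reduction. Short symptomatic non-electrolyte Grade 3 values would now do so, with no re-escalation.

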5.5.1.2. Mirvetuximab Soravtansine Dose Reduction Dose Levels

MIRV dose reduction will be as described in [Table 4](#).

Table 4: Mirvetuximab Soravtansine Dose Reduction Dose Levels

If the patient was receiving MIRV at:	Dose should be reduced to:
6.0 mg/kg AIBW	5.0 mg/kg AIBW
5.0 mg/kg AIBW	4.0 mg/kg AIBW
4.0 mg/kg AIBW	Permanently discontinue
Reduction of MIRV below 4.0 mg/kg will not be permitted. Dose re-escalation is not permitted.	

Abbreviations: AIBW = adjusted ideal body weight; MIRV = mirvetuximab soravtansine.

5.5.1.3. Monitoring and Management of Nausea and Vomiting

Treatment-related nausea (46% all grades; 1% \geq Grade 3) and vomiting (16% all grades; 1% \geq Grade 3) have been reported in patients treated with MIRV, despite premedication with dexamethasone. Therefore, it is recommended that an antiemetic (eg, 5-HT₃ serotonin receptor antagonists such as palonosetron, granisetron, or ondansetron) medication is provided before each MIRV dose ([Section 5.8.2](#)). Additional antiemetics may be used any time at the discretion

Document ID: CLIN-00067	Title: IMGN853-0419 Clinical Study Protocol	Version: 2.0
Legacy ID: 26587		Approved Date: 12/22/202

of the treating physician, according to institutional or other practice guidelines, American Society of Clinical Oncology (ASCO), European Society for Medical Oncology (ESMO), and NCCN. Patients should be advised to contact their treating physician at the first sign of vomiting or worsening nausea.

5.5.1.4. Monitoring and Management of Diarrhea

Mild to moderate diarrhea has been reported in patients treated with MIRV. Patients should be advised to contact their treating physician at the first sign of diarrhea. Patients may then be treated according to standard institutional practice. One suggested regimen would be the administration of loperamide 2 mg at the first sign of loose stool, with repeat dosing every two hours until symptoms resolve ([Wadler 1998](#)).

5.5.2. Ocular Disorders

Changes in visual acuity resulting from reversible keratopathy have been reported in other studies of DM4-containing immunoconjugates that use the SPDB linker ([Younes 2012](#)). Patients receiving MIRV in the Phase 1 and 3 trials (IMGN853-0401, IMGN853-0403) reported ocular AEs consistent with reversible keratopathy/corneal epitheliopathy.

5.5.2.1. Monitoring and Preventive Measures

In early dose escalation of Study IMGN853-0401, a relationship was observed between MIRV plasma exposure and likelihood of an ocular event and response. Exposure-response modeling suggested that a dose of 6.0 mg/kg AIBW provided adequate exposure for response while also maintaining overall exposure within a range that decreased the potential for ocular AEs. Due to the observation of ocular disorders consistent with reversible keratopathy/corneal epitheliopathy in patients treated with MIRV, ocular function will be carefully monitored. Ocular symptom assessments will be performed at baseline and at Day 1 of every cycle thereafter ([Table 2](#)). Complete ophthalmologic exams will be performed in all patients at baseline and every other cycle thereafter if there is a TEAE reported.

Patients are advised to avoid using contact lenses while on MIRV. Baby shampoo and a soft cloth should be used to clean the eyes, and a warm compress at bedtime may be used to decrease any possible inflammation on the eyelid's surface. Please refer to [Section 5.4.2.1](#) and [Section 5.4.2.2](#) for details on the prophylactic use of steroid eye drops and lubricating artificial tears. The use of UVA/UVB sunglasses is recommended in full daylight during the study. The use of temporary lower punctal plugs to increase lubrication of the eyes is optional if lubricating artificial tears and corticosteroid eye drops are not sufficient. If patients report signs or symptoms of ocular disorders, including, but not limited to, blurred vision or eye irritation, the management and dose modification guidelines outlined in [Table 5](#) should be followed.

5.5.2.2. Management and Dose Modification Guidelines

If a patient develops ocular symptoms of any grade, the patient is required to have a complete examination by an ophthalmologist. If a patient develops \geq CTCAE Grade 2 ocular symptoms, treatment with MIRV must be interrupted. Treatment should not be interrupted solely for Grade 2 ocular signs (eg, Grade 2 keratopathy) unless they are also associated with Grade 2 ocular

symptoms. Treatment with MIRV may resume if ocular symptoms improve to Grade 1 or baseline within 28 days of the next scheduled MIRV dose (refer to [Table 5](#) for details). If ocular symptoms last longer than 28 days, resumption of MIRV, with or without dose reduction, may be considered for those patients who have experienced clinical benefit if agreed upon between the Sponsor and the Investigator. Subsequent eye examinations will be scheduled to occur in every other cycle going forward, from the time that the AE was initially reported and at either the End of Treatment (EOT) Visit or 30-Day Follow-up Visit after treatment discontinuation, even if the results of the patient's ocular exam show no obvious clinical findings. Management of treatment-emergent ocular AEs with inflammatory characteristics should include corticosteroid eye drops and/or other measures as indicated by an ophthalmologist.

Table 5: Management of Ocular Symptoms

Severity Grade (CTCAE v5.0)	Management	Guidelines for MIRV Dose Modifications
Grade 1	Complete eye exam as outlined in Schedule of Assessments (Table 2) Monitor for worsening symptoms	Continue MIRV dosing
Grade 2	Complete eye exam as outlined in Schedule of Assessments (Table 2) Repeat complete exam as clinically indicated Patients should have weekly symptomatic ocular assessments by the Investigator until the symptoms resolve to Grade 1 or baseline or are deemed to be irreversible by the Investigator	Hold MIRV dosing until AE has resolved to Grade 1 or better Patients with ocular symptoms lasting < 14 days may be allowed to resume MIRV at the same dose level Patients with ocular symptoms lasting \geq 14 days but no more than 28 days may resume MIRV at one lower dose level Recurrence of Grade 2 toxicity on subsequent cycles despite best supportive care will require a MIRV dose reduction of one dose level
Grade 3	Complete eye exam as outlined in Schedule of Assessments (Table 2). Repeat complete exam as clinically indicated Patients should have weekly symptomatic ocular assessments by the Investigator until the symptoms resolve to Grade 1 or baseline or are deemed to be irreversible by the Investigator	Hold MIRV dosing Patients may be allowed to resume MIRV at a lower dose after AE has resolved to Grade 1 or better within 28 days Recurrence of Grade 3 toxicity on subsequent cycles despite best supportive care will require a MIRV dose reduction of one dose level
Grade 4	Complete eye exam as outlined in Schedule of Assessments (Table 2). Repeat complete exam as clinically indicated Patients should have weekly symptomatic ocular assessments by the Investigator until the symptoms resolve to Grade 1 or baseline or are deemed irreversible by the Investigator	Permanently discontinue MIRV

Abbreviations: AE = adverse event; CTCAE = common terminology criteria for adverse events; MIRV = mirvetuximab soravtansine.

Document ID: CLIN-00067	Title: IMGN853-0419 Clinical Study Protocol	Version: 2.0
Legacy ID: 26587		Approved Date: 12/22/202

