7.9. Ocular Symptom Assessment and Ophthalmic Examination

7.9.1. Ocular Symptom Assessment

Ocular symptom assessment will be performed before the start of each cycle by the treating physician or other qualified individual. For patients reporting CTCAE > Grade 1 ocular symptoms, study drug will be held until the patient is evaluated by an ophthalmologist for a complete examination. The ocular symptom assessment will also be performed at EOT and the 30-Day Follow-up visits. All SAEs, and those AEs assessed by the Investigator as at least possibly related to study drug, should continue to be followed until they resolve or stabilize, whichever comes first.

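### The 28-day ocular recovery limit in Protocol Section 5.5.2.2 and Table 5 has more than one starting point, so some patients fall under conflicting resumption rules

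*Protocol*

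**What the plan says.** Protocol Section 5.5.2.2 requires MIRV to be interrupted for ocular symptoms of Grade 2 or higher. It then gives two consecutive sentences on restarting.

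- The first: "Treatment with MIRV may resume if ocular symptoms improve to Grade 1 or baseline", with the limit "within 28 days of the next scheduled MIRV dose" and a pointer to Table 5 for details.
- The second: "If ocular symptoms last longer than 28 days, resumption of MIRV, with or without dose reduction, may be considered", but only "for those patients who have experienced clinical benefit if agreed upon between the Sponsor and the Investigator".

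Table 5, Grade 2, says "Hold MIRV dosing until AE has resolved to Grade 1 or better". It then sets the dose by how long symptoms lasted. Under 14 days, the same dose level is allowed. The next band covers symptoms of at least "14 days but no more than 28 days may resume MIRV at one lower dose level". Nothing is stated for longer durations.

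Table 5, Grade 3, allows a lower dose after recovery to Grade 1 or better inside 28 days, without saying from when the 28 days run.

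Section 7.9.1, repeated in Table 2 footnote l, says that for symptoms above Grade 1 "study drug will be held until the patient is evaluated by an ophthalmologist for a complete examination". It gives no recovery grade and no time limit.

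**The concern.** The first resumption sentence ties the 28 days to a dosing date. The second sentence and the Grade 2 row of Table 5 tie them to the length of the symptoms. With a three-week cycle these are different limits for nearly every onset date. A site that follows the first sentence would restart some patients with no further step. A site that follows the second would need clinical benefit and an agreement with the Sponsor for the same patients.

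About 75 centers are planned, so both readings can be expected in practice. SAP Section 7.2 tabulates TEAEs leading to dose modification and to drug withdrawal, and groups ocular TEAEs for focused review. Those tables would then partly reflect which sentence each site followed.

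**Working it through.** The plan states no figure to reproduce. The check compares the rules and then counts days.

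**The rules side by side**

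| Source (Protocol) | Limit | Counted from | What it allows |
|---|---|---|---|
| 5.5.2.2, first resumption sentence | 28 days | next scheduled dose | resume at Grade 1 or baseline |
| 5.5.2.2, next sentence | over 28 days | symptom duration | resume, with or without dose reduction, given clinical benefit and agreement |
| Table 5, Grade 2 | under 14; 14 to 28 days | symptom duration | same level; one level lower; nothing beyond 28 |
| Table 5, Grade 3 | 28 days | not stated | lower dose |
| 7.9.1 and Table 2 footnote l | none | none | hold until ophthalmologist evaluation |
| Table 3 footnote a and 5.5.6 | 21 days | missed dose | general limit; gives way to toxicity-specific guidance |

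**Day count**

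Inputs: dosing on Day 1 of a 21-day cycle (Section 4.1.2), so the next dose is due on Day 22. Two assumptions, neither defined in the protocol: the next scheduled dose is the first one due after onset, and duration runs from onset of the symptoms that trigger the hold to recovery to Grade 1 or baseline.

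- Last day under the dose-based limit: 22 + 28 = Day 50.
- Longest symptom duration it admits: 50 − onset day.
- Longest under the duration limit: 28 days.
- Gap: (50 − onset day) − 28 = 22 − onset day.

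| Onset | Dose-based limit admits | Duration limit | Gap |
|---|---|---|---|
| Day 1 | 49 days | 28 | 21 |
| Day 2 | 48 days | 28 | 20 |
| Day 8 | 42 days | 28 | 14 |
| Day 15 | 35 days | 28 | 7 |
| Day 22 | 28 days | 28 | 0 |

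The two limits meet only at onset on Day 22. If the phrase meant the following dose instead, Day 50 would move 21 days later and every gap would widen by 21 days.

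**A patient in the gap**

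Grade 2 symptoms start on Day 8 and recover to Grade 1 on Day 43. Duration is 43 − 8 = 35 days. Recovery comes 43 − 22 = 21 days after the scheduled dose.

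- First resumption sentence: 21 ≤ 28, so MIRV may resume.
- Next sentence: 35 > 28, so it may resume only with clinical benefit and agreement.
- Table 5, Grade 2: 35 days lies in neither band, so no dose level is given.

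For contrast, with the same onset, recovery on Day 31 (23 days of symptoms, 9 after the scheduled dose) satisfies both limits. Recovery on Day 53 (45 days, 31 after) fails both.

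**The case against.** The strongest reply is that the provisions can be read together. The first sentence refers to Table 5 for details, and Section 5.5.2.1 says Table 5 should be followed. Table 5 counts duration in its Grade 2 row, and so does the second sentence, so the first sentence could be treated as general wording that the specific rules limit. This narrows the ambiguity but does not remove it. The Grade 2 row stops at 28 days and so cannot supply the detail for a patient whom the first sentence lets resume later. The Grade 3 row names no starting point. The general 21-day limit is itself counted from a dose, so a dose-based reading of the first sentence is a natural one.

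Three stronger readings are tempting, and the documents do not support them.

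- A reader might infer that a patient in the gap is eligible under one rule and barred under another. The second sentence keeps a route open, so the conflict is between resuming without agreement and resuming only with it.
- A reader might infer that Section 7.9.1 and footnote l release the hold once the eye examination is done. They contain no clock, and they read naturally as a step added to the recovery condition in Section 5.5.2.2. The recovery criteria in Section 5.5.1 are not a clean backstop, because they are introduced as applying when no TEAE requires dose modification. That justifies a cross-reference and no more.
- A reader might size the problem by the 40% rate of blurred vision in Section 1.5.2, or call it the most common toxicity. That section puts nausea at 51% and diarrhea also at 40%, and describes the profile as mainly low grade. The documents give no rate for Grade 2 or higher symptoms lasting more than 28 days, which is the only group affected.

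It also stands that the first sentence and Table 5 both require recovery before restarting. The choice between those two clocks does not by itself permit dosing through unresolved Grade 2 or higher symptoms.

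**Conclusion.** The inconsistency is real and lies within Section 5.5.2.2 and Table 5. One 28-day limit is counted from a dose, another from symptom duration, and a third has no stated origin. On the assumption that the next scheduled dose is the first due after onset, the first two differ by 0 to 21 days, depending on when in the cycle symptoms begin. Patients whose recovery falls in that interval meet conflicting conditions for restarting, and the Grade 2 row gives them no dose level.

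The number of such patients cannot be derived from the documents. The consequence is uneven handling of Grade 2 and 3 ocular symptoms, and some site-dependence in the single-arm, descriptive summaries of dose modification and discontinuation. ORR, its test, alpha and power are not affected.

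**What to change.** The sponsor should reconcile Section 5.5.2.2 with the Grade 2 and Grade 3 rows of Table 5. One starting point for the 28 days should be used throughout, and every patient allowed to resume should fall under a stated rule, including the dose level. If the limit stays tied to a dose, the protocol should define which dose is meant. Which rule is clinically right is for the sponsor to decide, and none is proposed here.

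As a secondary wording point, Section 7.9.1 and Table 2 footnote l should cross-refer to the recovery condition in Section 5.5.2.2, so that the examination is not taken as the only condition for restarting.

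The cost is a clarification letter or a few lines of amendment text. No statistical design or analysis section needs to change.
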